weekly basis. This weekly visit will serve several purposes: (1) to download data from the actiwatch (verify sleep duration); (2) to charge the watch; (3) to obtain weekly diaries (verify bedtimes and wakeup times) and other questionnaires; (4) to obtain body weight, waist circumference, and blood pressure measurements and blood samples (bi-weekly only). Participants will be told a priori, as part of the screening process, that they must adhere to the sleep protocol for continued participation in the study and that adherence will be checked weekly. Non-adherent participants will be terminated from the study. Adherence will be defined as having bedtimes and wake times within 30 min of scheduled times at least 5 days/week and achieving an average of >7 h of sleep each week with no more than one night of sleep <7 h during the HS phase and achieving an average sleep reduction of 1.5 h from screening sleep duration each week with no more than 1 night with <1.5 h of restriction during the SR phase. Daytime naps will not be permitted. Participants will receive weekly incentives, in the form of a gift card, for their continued adherence to the sleep protocol.

Blood sampling procedures.

Fasting blood samples will be taken at baseline, 3 weeks, and endpoint of each sleep phase for the measurement of metabolic risk factors: glucose, insulin, and inflammatory markers *. An oral glucose tolerance test will be performed at baseline and endpoint as well. Two baseline blood samples (8 mL) will be obtained at 10 and 5 min before glucose ingestion (-10 and -5). At time 0, participants will consume 75 g of glucose in 300 mL solution orally. Subsequent blood samples (10 mL) will be obtained at 15-, 30-, 60-, 90- and 120-min post-intake. These procedures will be performed by a certified nurse in the CRR at CUMC.

Details of the outcome measures

Blood pressure measurements.

Blood pressure will be measured weekly with the participant sitting, with their legs uncrossed, for at least 5 min. Measurements will be taken twice from the non-dominant arm using an appropriately sized cuff. In addition, participants will wear a blood pressure monitor for 24 h at baseline, 3 weeks, and 6 weeks of each intervention xi.

Body composition measures.

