an ELISA (R&D Systems, Inc., Minneapolis, MN), using 200 uL sera. The manufacturer indicates that the tumor necrosis factor-α assay has an approximate minimal detectable concentration of 0.12 pg/mL. Interleukin-6 will be assessed with an ELISA (R&D Systems, Inc., Minneapolis, MN) using 200 uL sera. High-sensitivity C-reactive protein will be assessed with an ELISA (ALPCO Diagnostics, Windham, NH). Serum samples will be diluted 1:100 prior to use. *Lifestyle behavior assessments*.

We will also assess physical activity level by waist actigraphy (GT3X+ Actigraph LLC, Pensacola, FL) throughout each study phase xiii. We hypothesize that total energy expenditure and physical activity level will be lower during the period of SR compared to HS.

Throughout the study, participants will self-select their food intake in a free-living situation. Food intake will be assessed at baseline and endpoint by 3-day food records (2 weekdays and one weekend day). Energy and macronutrient intakes from the food records will be assessed using the University of Minnesota Nutrition Data System for Research (NDSR, Minneapolis, MN).

Statistical analysis plan

Exploratory data analysis for all response variables will be performed using R, SAS and other software. As part of the analysis, we will compute descriptive statistics for each variable. In particular, the proportion, mean, variance, standard error and the range of continuous variables and frequency and model for discrete variables will be computed. Descriptive statistics will be computed for each specific sleep. In addition, correlation coefficients between the variables will be computed and scatter plots will be checked for linear relationships. The correlations and scatter plots help assess the degree of collinearity among the variables, which will be useful for the interpretation of regression-based linear mixed model analyses discussed later. The data will be tested for normality, and if needed an appropriate transformation will be used on the raw data to make the normal approximation better.

As we are collecting data from two phases for each subject, we will test for phase effect by using phase main effect term in an initial version of each linear model. If the term is not found to be significant then we will rebuild the linear model without the term.

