Linear Mixed Model Analyses. We will fit a linear mixed model to analyze the data. Treatments (sleep: SR vs. HS) will be used as fixed effects and subject will be used a random effect. The other independent variables (covariates) will be age, baseline BMI, and race/ethnicity. If required anywhere in the analysis plan, p-values will be adjusted for multiple comparisons.

Specific Aim 1. To assess the effects of SR on cardio-metabolic risk profile, relative to HS. (Hypothesis 1: Prolonged SR will lead to increased blood pressure and reduce glucose tolerance relative to HS.) We will perform a repeated measure linear mixed model analyses separately with each of blood pressure and glucose tolerance measures (each in a separate model) as the response and sleep (SR vs. HS), time, sleep-time interaction and the covariates as independent variables, with data from all time points combined. Subject will be used as a random effect. Additionally, we will also use the change from baseline to week-6 in each of blood pressure and glucose tolerance measures as response variables in separate regressions, where sleep (SR vs. HS) and the covariates will be used as the independent variables. Paired one-sided t-test and Wilcoxon test will be used to determine whether the SR is associated with increased blood pressure and reduced glucose tolerance vs. HS.

Specific Aim 2. To assess the effects of SR on adiposity, relative to HS, over a 6-week period. (Hypothesis 2: Prolonged SR will lead to increased visceral adiposity, assessed by MRI, relative to HS.) We will perform a repeated measure linear mixed model analyses separately with each visceral adiposity variable (as observed by MRI) (each in a separate model) as the response and sleep (SR vs. HS), time, sleep-time interaction and the covariates as independent variables, with data from all time points combined. Subject will be used as a random effect. Additionally, we will also use the change from baseline to week 6 in each adipose tissue variable as response variables in separate regressions, where sleep (SR vs. HS) and the covariates will be used as the independent variables. Paired one-sided t-test and Wilcoxon test will be used to determine whether the SR is associated with increased adiposity variable relative to HS.

_

xiii See Amendment 2a

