Specific Aim 3. To assess the effects of SR on diet and physical activity level. (Hypothesis 3a: Prolonged SR will lead to reduced physical activity relative to HS.) We will perform a repeated measure linear mixed model analyses separately with each physical activity measure (each in a separate model) as the response and sleep (SR vs. HS), time, sleep-time interaction and the covariates as independent variables, with data from all time points combined. Subject will be used as a random effect. Additionally, we will also use the change from baseline to week-6 in each physical activity measure as response variables in separate regressions, where sleep (SR vs. HS) and the covariates will be used as the independent variables. Paired one-sided t-test and Wilcoxon test will be used to determine whether the SR is associated with reduced physical activity measures relative to HS. (Hypothesis 3b: Diet quality will be reduced with SR relative to HS, as reflected by increased intake of snacks, fat, and simple sugars.) We will perform a repeated measure linear mixed model analyses separately with each diet quality measure (snacks, fat, and simple sugars intakes, each in a separate model) as the response and sleep (SR vs. HS), time, sleep-time interaction and the covariates as independent variables, with data from all time points combined. Subject will be used as a random effect. Additionally, we will also use the change from baseline to week-6 in each diet quality measure (snacks, fat, and simple sugars intakes) as response variables in separate regressions, where sleep (SR vs. HS) and the covariates will be used as the independent variables. Paired one-sided t-test and Wilcoxon test will be used to determine whether the SR is associated with reduced diet quality measure (i.e., increased snacks, fat, and simple sugars intakes) relative to HS.

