 - c. Fasted blood draws occurred at Baseline, Week 3, and Endpoint study visits, rather than biweekly, to reduce participant burden.
 - d. An additional fasted blood draw was added at the Week 4 study visit of each phase.
 - e. Frequency of ambulatory blood pressure monitoring was reduced to one endpoint measure to reduce participant burden and in response to participant complaints about this measure.
 - f. Blood samples were analyzed by the Biomarkers Core Laboratory of the Irving Institute for Clinical and Translational Research.

REFERENCES

- 2. Johns MW. A new method for measuring daytime sleepiness: the Epworth sleepiness scale. Sleep 1991;14(6):540-5. doi: 10.1093/sleep/14.6.540.

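### The paired t and Wilcoxon tests for Aims 1–3 never adjust for phase, and the linear models drop it when it is not significant; keeping it costs almost nothing

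*Combined protocol and SAP*

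**What the plan says.** The Statistical analysis plan section tests for a phase effect "by using phase main effect term in an initial version of each linear model" and adds "If the term is not found to be significant then we will rebuild the linear model without the term". That rule covers linear models only.

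For each aim the plan also names simple paired tests:
- Aim 1: "Paired one-sided t-test and Wilcoxon test will be used to determine whether the SR is associated with increased blood pressure", and likewise for glucose tolerance.
- Aim 2: "Paired one-sided t-test and Wilcoxon test will be used to determine whether the SR is associated with increased adiposity variable relative to HS".
- Aim 3: "Paired one-sided t-test and Wilcoxon test will be used to determine whether the SR is associated with reduced physical activity measures relative to HS", with the same wording for diet quality.

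None of these tests contains phase or sequence, and no other section adjusts them. For Aim 1, "we will also use the change from baseline to week-6 in each of blood pressure and glucose tolerance measures as response variables" describes the change-score regressions; Aims 2 and 3 have matching ones. The plan does not say whether the paired tests use six-week changes or endpoint values.

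The documents also do not give the allocation ratio, any blocking, the alpha, the level of the phase pre-test, or a plan to report completers by sequence.

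**The concern.** In a two-period crossover, a phase effect enters the within-woman SR–HS difference with opposite signs in the two sequences. Leaving it out has two consequences. First, it widens the spread of the paired differences, so the paired tests lose power even when the sequences are perfectly balanced. Second, if completers are unevenly split between sequences, part of the phase effect moves into the SR–HS estimate. Since 80 women are to be enrolled and 50 are expected to complete, the split among completers can be uneven even if allocation was balanced.

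The repeated-measures models raise a further point. There the sleep-time interaction carries the treatment contrast, and a phase main effect does not adjust an interaction; phase-by-time does. In the change-score regressions a phase main effect is the right term and only has to be kept. The same is true of ambulatory blood pressure after amendment 2e ("Frequency of ambulatory blood pressure monitoring was reduced to one endpoint measure"), read here as one measure per phase.

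**Working it through.** **The plan's own figure.** From the sample size section, 0.69/0.36 = 1.92 (fat mass) and 0.91/0.65 = 1.40 (weight gain). With 50 pairs, paired-t power exceeds 99.99% for both, so the stated figure of more than 80% holds. At these effect sizes the treatment of phase makes no practical difference. The documents give no effect size for visceral fat, blood pressure or glucose tolerance.

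**Inputs.** From the documents: two phases, 80 enrolled, 50 completers, one-sided paired tests. Assumed: 5% one-sided alpha, a 5% two-sided phase pre-test, a true effect τ = 0.36 SD (about 80% power at N = 50), and a phase effect π of 0 to 0.5 SD. The unit is the SD of the SR–HS difference within a sequence. π acts on the analysed quantity: the six-week change, or the level for ambulatory blood pressure.

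**Model.** The mean difference is τ − π for SR-first women and τ + π for HS-first women. Therefore:
- Shift in an unadjusted estimate = π × (n HS-first − n SR-first)/N. At 20 SR-first/30 HS-first and π = 0.3, this is 0.3 × 10/50 = 0.060 SD.
- Apparent SD at 25/25 = √(1 + π²), which is 1.044 at π = 0.3 and 1.118 at π = 0.5.
- SE ratio with phase kept = 1/√(1 − b²), where b is the difference between the sequence counts divided by N. It is 1.000 at 25/25, 1/√(1 − 0.12²) = 1.007 at 22/28, and 1/√(1 − 0.2²) = 1.021 at 20/30.

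**Averaged over chance splits** (200,000 simulated trials per cell, mean bias at most 0.0005 SD). Power at τ = 0.36:

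| Allocation | π | Paired t | Test, then drop | Phase kept |
|---|---|---|---|---|
| 40/40 | 0 | 80.7% | 80.7% | 80.3% |
| 40/40 | 0.1 | 80.4% | 80.6% | 80.4% |
| 40/40 | 0.3 | 78.3% | 80.1% | 80.4% |
| 40/40 | 0.5 | 73.7% | 80.2% | 80.3% |
| Simple | 0 | 80.7% | 80.7% | 80.0% |
| Simple | 0.3 | 77.6% | 79.6% | 79.9% |
| Simple | 0.5 | 72.6% | 79.8% | 80.0% |

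Type I error is 4.0–5.1% for the paired t, 5.0–5.2% for test-then-drop and 4.9–5.1% with phase kept. Under 40/40, the signed-rank test has 76.3% power at π = 0.3 and 71.2% at π = 0.5; the period-adjusted rank-sum test has 78.5% and 78.2%.

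**Conditional on one realised split, π = 0.3** (paired t / test-then-drop / phase kept):

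| SR-first/HS-first | Bias (SD) | Type I error | Power |
|---|---|---|---|
| 20/30 | +0.060 / +0.017 / 0 | 9.7 / 6.8 / 5.0% | 89 / 82 / 79% |
| 30/20 | −0.060 / −0.017 / 0 | 1.7 / 4.4 / 5.1% | 65 / 76 / 79% |
| 22/28 | +0.036 for paired t | 7.1 / 5.8 / 5.0% | – |
| 28/22 | −0.036 for paired t | 2.4 / 4.4 / 4.9% | – |

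(0.3 × 6/50 = 0.036.) The chance of a split at least this extreme in the inflating direction is 1.8% (40/40) or 10% (simple) for 20/30, and 12% or 24% for 22/28.

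**Repeated-measures models.** A generalised least squares calculation with a random subject effect and complete data took a 0.3 shift in the phase-2 six-week change at a 20/30 split. The bias in the sleep-time term is 0.060 without phase, still 0.060 with a phase main effect, and 0 with phase-by-time. A pure level shift gives no bias in any of the three. A mixed model that also uses women with one phase only would not follow the completer formula exactly.

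**The case against.** The strongest reply is that little harm is shown. Randomisation makes the shift zero on average, and nothing in the documents suggests loss related to sequence, because every completer must pass both conditions in one order or the other. Each phase has its own baseline, so a constant level shift cancels from change scores; only a different six-week drift between phases remains, after a washout of generally six weeks. The assumed π is also large relative to the effect: 0.3/0.36 is 83% of it, and 0.5 exceeds it. At π = 0.1 adjustment only breaks even. The drop rule itself costs at most 0.4 points of average power under 40/40 and is slightly ahead at π of 0 and 0.1, since the pre-test detects a phase effect of 0.5 SD in about 93% of trials and 0.3 SD in about 54%. Nor is adjustment entirely free: at 20/30 with π = 0, keeping phase costs about 1.4 points of power (80.5% to 79.1%).

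Most of this stands and limits the claim. It does not help the paired tests, which have no protection once a phase effect is present. The baseline argument applies to them only if they use within-phase changes, which the plan does not say; with endpoint values the exposure is larger. Endpoint-only ambulatory blood pressure has no phase baseline at all.

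**Conclusion.** The concern holds as a cheap improvement, not as a serious flaw. No systematic bias or general type I inflation is claimed. At an assumed phase effect of 0.3–0.5 SD and a moderate treatment effect, keeping phase gains about 2–7 points of power over the paired t-test. It costs 0.4–0.7 points on average if there is no phase effect. It also removes the dependence of the result on the realised sequence split. The unadjusted paired tests are the main gap; test-then-drop matters little except with an uneven split and a moderate phase effect.

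These sizes rest on the assumed phase effect, alpha, treatment effect and splits, none of which the documents give, and on reading the paired tests as analyses of six-week changes. Confidence is medium. The change is worth making because it is nearly free, not because the expected effect is large.

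**What to change.** Delete the rule that rebuilds the model without phase. Suggested text:

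> Phase (1 vs 2) will be a fixed effect in every change-score and endpoint-only SR–HS model regardless of its p-value. Repeated-measures models will also include phase-by-time. The paired t and Wilcoxon comparisons will be period-adjusted: within-woman phase 1 minus phase 2 differences will be compared between the two sequences by two-sample t and rank-sum tests. Completers will be reported by sequence.

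State also whether these comparisons use six-week changes or endpoint values.

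**Cost.** The change-score models, endpoint-only models and paired comparisons lose one degree of freedom, and the SE rises by 0% at 25/25, 0.7% at 22/28 and 2.1% at 20/30. For seated blood pressure ("Blood pressure will be measured weekly with the participant sitting"), with time as a factor at baseline plus six weeks, the fixed effects without phase number 2 × 7 = 14, covariates aside. Phase adds 1 and phase-by-time adds 6, giving 21, with the same 0–2.1% SE increase on the week-6 sleep-time term.

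The amendments section already describes accrued participants. If the data have been analysed, label the change post hoc and report the period-adjusted results beside the planned tests.

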Study Title: Impact of Sleep Restriction on Cardiometabolic Risk Factors in Pre- and Postmenopausal Women

Short Title: Impact of Sleep Restriction in Women

ClinicalTrials.gov ID: NCT02835261

Document Date: 2016 February 16 (original); 2020 July 21 (final revision); 2025 October 09

(submitted)

SPECIFIC AIMS

The overall goal of this project is to test the hypothesis that long-term, sustained SR, in women, will lead to increased cardio-metabolic risk. This will be characterized by increases in visceral adiposity, unhealthy lifestyle behaviors (poor dietary quality and low physical activity) and cardio-metabolic risk factors (blood pressure, glucose intolerance) relative to HS. We expect these changes to be worse in pre- compared to post-menopausal women.

Specific Aim 1. To assess the effects of SR on cardio-metabolic risk profile, relative to HS.

Hypothesis 1: Prolonged SR will lead to increased blood pressure and reduced glucose tolerance relative to HS.

Specific Aim 2. To assess the effects of SR on adiposity, relative to HS, over a 6-week period. *Hypothesis 2:* Prolonged SR will lead to increased visceral adiposity, assessed by magnetic resonance imaging (MRI), relative to HS.

Specific Aim 3. To assess the effects of SR on diet and physical activity level.

Hypothesis 3a: Prolonged SR will lead to reduced physical activity relative to HS.

Hypothesis 3b: Diet quality will be reduced with SR relative to HS, as reflected by increased intake of snacks, fat, and simple sugars.

Exploratory Hypothesis: The effects of prolonged SR on adiposity and cardio-metabolic risk factors will be greater in pre-menopausal women relative to post-menopausal women.

RESEARCH DESIGN & METHODS

Study population & Sample size determination

We will enroll 80 participants and expect 50 to complete the study. This drop-out rate accounts for participant non-compliance and withdrawal from the study. In our previous *Sleep Study*, our completion rate was 90% (27/30). We expect a larger drop-out rate in the proposed study due to the longer duration of each treatment phase, and also, some participants may be dismissed from the study from their inability to achieve and maintain the 1.5 h average weekly SR.

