In this proposed study, each participant will undergo 2 study phases, and each response variable will be measured *at least* once per phase. Thus, for each response measure we will have at least 50×2 paired observations. Based on preliminary data analysis, we have estimated an effect size (mean paired difference) of 0.69 ± 0.36 g for fat mass and an effect size (mean paired difference) of 0.91 ± 0.65 g for weight gain. This translates to very large effect sizes of 1.92 (fat mass) and 1.4 (weight gain) for paired t-tests. With these effect sizes we will have >80% power for paired t-tests with our expected sample size and will have sufficient power to test for differences between pre- and post-menopausal women.

Eighty pre- and postmenopausal women, age 20-65 y i with an overweight BMI (25-29.9 kg/m²) ii will be recruited from the New York City area. These women will come from the pool of participants in the Population Science project in this Center application. Pre-menopausal women will not be on oral contraceptive medications and post-menopausal will not be on hormone replacement therapy. In addition, women recruited to participate in this study will habitually sleep 7-9 h/night, will be free of any current and past sleep and psychiatric disorders, including eating disorders (ex. anorexia, bulimia, night eating syndrome), and will not have type 2 diabetes or CVD (**Table 2**) iii. We will exclude women taking medication to reduce blood pressure and cholesterol levels. Smokers (defined as currently smoking any cigarettes or ex-smokers <3 y), non-day and rotating shift workers, persons who plan to travel across time zones within 4 weeks of the study, and those with a history of drug and alcohol abuse, drowsy driving, or excessive caffeine (>300 mg/d) or alcohol intakes >2 drinks/day) will also be excluded. Further, we will not enroll women who have had a recent weight change or who actively participated in a diet or weight loss program in the previous 3 mo, and those with a neurologic condition that may disrupt the procedures. Women who are pregnant or <1 y post-partum, and those with contraindications for MRI scanning will be excluded iv. All participants will have normal scores on the

ⁱ See Amendment 1b

ii See Amendment 1c

iii See Amendment 1d

iv See Amendment 1a

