This study will be a randomized, crossover, outpatient SR study with 2 phases of 6 weeks each. Sleep duration in each phase will be the participant's regular bed- and wake-times during the HS phase and HS minus 1.5 h in the SR phase. During the HS phase, participants will be asked to follow a fixed bedtime routine based on their screening sleep schedule. During the SR phase, participants will be asked to keep their habitual wake time constant but delay their bedtime to achieve a reduction of 1.5 h in total sleep time. A delay in bedtimes was chosen rather than advancing wakeup time because it likely most closely reflects differences in sleep timing behavior between short and normal sleepers. Spaeth and colleagues have also shown that restricting sleep to the latter portion of the night is associated with increased food intake and weight gain relative to HS (8). We also considered providing fixed bed- and wakeup times for all women but decided to provide individualized bedtimes and wakeup times to reduce variability in our sample.

On the first day of each study phase (baseline), participants will come to the Clinical Research Resource (CRR) of the Irving Center for Clinical and Translational Research (CTSA) at CUMC in the morning after an overnight, 12 h fast. Participants will have anthropometric measurements taken and will then be taken to the department of Radiology to undergo magnetic resonance imaging (MRI) scanning to assess body composition. They will then return to the CRR for an oral glucose tolerance test. Participants will begin the fixed bedtime routine that night. These baseline measurements will be

repeated at endpoint, 6 weeks later. Body weight and waist circumference will be measured weekly and fasting blood samples will be taken bi-weekly during adherence check visits v.

Recruitment and blinding

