Women who fit the general inclusion/exclusion criteria for this study will be identified from the Population Science project and invited to participate in this project. Women who express an interest in participating will undergo a preliminary phone screening. During this phone interview, more details of the study will be provided to the prospective participant and additional information will be obtained to determine potential eligibility. Women who pass the phone screening and are interested in participating in the study will be scheduled for an in-person screening. At this second screening point, eligibility will be ascertained. From there, sleeping behavior will be established. This will be done with actigraphy over a 2-week period.

Two weeks prior to randomization and during the washout period, participants will wear an actigraph (Micro Motion Logger Sleep Watch, Ambulatory Monitoring, Inc., Ardsley, NY) vi and keep a sleep diary to verify sleep duration and sleep-wake schedule. In addition to achieving an average sleep of 7-9 h/night, by wrist actigraphy. participants will only be enrolled if they achieve 7 h of sleep for at least 10 of the 14 nights of screening and have <4 nights with <6 h of sleep vii. At the time of randomization, a urine pregnancy test and drug screen will be performed. Participants will be asked to abstain from caffeine and alcohol intake for 24 h prior to the start of each study phase. Between study phases, if participants have not returned to baseline sleep patterns, an additional 2-4 week washout period will be provided. In general, washout periods will be 6 weeks in duration. This washout length will ensure that women are in the same phase of their menstrual cycle at the start of each experimental phase (Fig. 3).

[figure not shown]

Figure 3. Study protocol. Participants will undergo a 2-wk screening to assess eligibility prior to randomization to their first study phase: restricted or habitual sleep. At baseline, body composition will be assessed and blood samples will be taken. Compliance with the sleep protocol will be assessed weekly, along with weight measurements. A blood sample will be taken bi-weekly. Baseline measurements will be repeated at endpoint (6 wk). Participants will undergo a 6-wk washout period before undergoing phase 2.

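### The Aims 1–3 repeated-measures model pools baseline with follow-up and names subject as its only random effect, so its standard errors are wrong if women vary between phases

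*Combined protocol and SAP*

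**What the plan says.** The design section states: "This study will be a randomized, crossover, outpatient SR study with 2 phases of 6 weeks each". On the gap between phases, the recruitment section says: "In general, washout periods will be 6 weeks in duration". The two phase baselines are therefore about 6 + 6 = 12 weeks apart.

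The general paragraph on linear mixed models reads: "Treatments (sleep: SR vs. HS) will be used as fixed effects and subject will be used a random effect". Aims 1, 2 and 3 then each prescribe the same repeated-measures model, with sleep, "time, sleep-time interaction and the covariates as independent variables, with data from all time points combined. Subject will be used as a random effect". Baseline of each phase is one of those time points.

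Visits per phase differ by outcome:
- MRI, the oral glucose tolerance test and food records: baseline and endpoint only.
- Clinic pressure: "Blood pressure will be measured weekly with the participant sitting".
- Ambulatory pressure: a single endpoint reading since Amendment 2e.

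A fixed phase term is tried and dropped if not significant. Each Aim also lists a regression of the baseline-to-week-6 change, and one-sided paired t and Wilcoxon tests. None of these analyses is ranked, and the paired tests are not said to use change scores.

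**The concern.** A single random intercept per woman treats any two of her readings as equally alike, whether from the same phase or from different ones. If a woman's level shifts between phases, that shift goes into the residual. The residual is then too small for comparing phase averages (the sleep main effect) and too large for comparing changes within a phase (sleep-by-time). Baseline is also pooled, so a sleep effect averaged over visits includes a visit at which the intervention cannot yet have acted.

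At stake are the false-positive rate if the averaged sleep term is read, and power if the interaction is read for the MRI, glucose tolerance and diet outcomes. The mixed model comes first in every Aim, so its intervals may well be the ones reported.

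**Working it through.** **The plan's own figure.** On numbers, the sample-size section says: "We will enroll 80 participants and expect 50 to complete the study". Its first planning value is this: "effect size (mean paired difference) of 0.69 ± 0.36 g for fat mass". That gives 0.69/0.36 = 1.92, as stated. Its second is this: "effect size (mean paired difference) of 0.91 ± 0.65 g for weight gain". That gives 0.91/0.65 = 1.40, also as stated. With 50 women the power of a paired t-test is close to 100%, which agrees with the claim of more than 80%. That claim concerns paired t-tests, not the mixed model, and is unaffected.

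**Model for the check.** Reading = woman + woman-by-phase (variance sp²) + residual (variance se²), with T visits per phase. Both variances are assumptions. Alpha is not stated; two-sided 5% is assumed.

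With a subject-only intercept and balanced data, the expected residual mean square is se² + T·sp²/(2T − 1). The correct error is se² + T·sp² for the sleep main effect and se² for sleep-by-time. Actual size is 2·[1 − Φ(1.96/√ratio)], where ratio = correct error ÷ model residual.

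**Two visits (T = 2), residual SD 0.5, so se² = 0.25**

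| Woman-by-phase SD | Model residual | Interaction SE too large by | Interaction size | Power if truly 80% | Main-effect ratio | Main-effect size |
|---|---|---|---|---|---|---|
| 0 | 0.25 | none | 5% | 80% | 1.00 | 5% |
| 0.3 | 0.25 + (2/3)(0.09) = 0.31 | √(0.31/0.25) = 1.11, 11% | 2.9% | Φ(2.80 − 1.96 × 1.11) = 73% | 0.43/0.31 = 1.39 | 9.6% |
| 0.5 | 0.25 + (2/3)(0.25) = 0.417 | √(0.417/0.25) = 1.29, 29% | 1.1% | Φ(2.80 − 1.96 × 1.29) = 61% | 0.75/0.417 = 1.80 | 14.4% |

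An effect δ seen only at week 6 enters the averaged main effect as (0 + δ)/2 = δ/2.

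**Weekly clinic pressure (T = 7: baseline plus six weeks, assumed), residual SD 0.6, so se² = 0.36**

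| Woman-by-phase SD | Main-effect ratio | Main-effect size |
|---|---|---|
| 0.2 | 0.64/0.382 = 1.68 | 13% |
| 0.3 | 0.99/0.408 = 2.42 | 21% |
| 0.5 | 2.11/0.495 = 4.27 | 34% |

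**Serial correlation at seven visits.** Take AR(1) residuals with correlation 0.6 (assumed) and unit residual variance. If time is linear, simulated size of the subject-only interaction test is about 15%, 12% and 7% when woman-by-phase variance is 0, 20% and 50% of the within-woman total. This is too liberal, the opposite of the two-visit result.

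A woman-within-phase intercept alone does not cure this. For the categorical week-6-minus-baseline contrast, the correct variance factor is 1 − 0.6⁶ = 0.953. The model uses 1 − 0.326 = 0.674, where 0.326 is the mean pairwise correlation. The ratio is 1.41 and the size about 10%.

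**With a correct error term** (a within-woman comparison, or woman-by-phase modelled where that is the only extra source), simulated size was 4.5–5.4% in every scenario run.

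**The case against.** **The plan has other analyses.** The change-score regression and paired tests are there, the wording that decides each hypothesis is attached to the paired tests, and the power statement is for paired t-tests. A paired test on within-phase changes removes the woman-by-phase level and is correctly sized. This stands: the fault lies in one of several analyses. But nothing ranks them, and nothing says the paired tests use changes.

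**The variance is unknown.** This stands too. A reader might infer that the reported intervals must be wrong whichever term is read. The documents do not support that, because at zero woman-by-phase variance, and without serial correlation, both tests hold 5%. In the two-visit case they then also have equal power, so dilution alone costs nothing.

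**Phase 1 endpoint and phase 2 baseline are only about 6 weeks apart,** as close as baseline and endpoint within a phase. That is true, but for two visits it does not reverse the directions. Suppose correlation merely decays with time, r₁ ≥ r₂ ≥ r₃ at 6, 12 and 18 weeks. Correct minus model variance, per woman and per unit variance, is −(8/3)(r₂ − r₃) ≤ 0 for the interaction and 4r₁ − (8/3)r₂ − (4/3)r₃ ≥ 0 for the main effect.

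**The model label could cover a residual covariance,** and the plan does not say that the averaged sleep term will be tested. With baseline as the reference visit, the sleep coefficient is just the baseline difference. Both points are fair, but the only dependence named is subject, and the test is left open. The fixed phase term does not help, since it shifts the mean and does not describe how individual women differ between phases.

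**Two further over-readings.** The interaction test is not over-conservative for every outcome, as the serial-correlation case shows. Nor is the main effect halved for every outcome: with seven visits and a constant post-baseline effect, 6/7 is retained.

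**Conclusion.** The point holds conditionally. Taken as written, the model misstates standard errors whenever woman-by-phase variance is above zero, which is plausible with phase baselines about 12 weeks apart.

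- **Two-visit outcomes** (residual SD 0.5, woman-by-phase SD 0.3–0.5): the interaction test loses roughly 7 to 19 points of an 80% power. The averaged main effect has about twice to three times the nominal error and estimates half of a week-6 effect.
- **Weekly clinic pressure** (residual SD 0.6, woman-by-phase SD 0.2–0.5): the averaged main-effect test rejects a true null in about 13–34% of trials. The interaction test may err in either direction, depending on how time is coded and on serial correlation.
- **Ambulatory pressure** is outside the point: it has one endpoint reading per phase, so there is no baseline to pool and no interaction to fit.

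All SDs, the AR(1) value and alpha are assumptions, so the ranges illustrate and do not predict. The documents do not support the inference that the trial's conclusions as a whole are invalid, because correctly sized analyses are available in the plan if they are run on within-woman changes. This should be corrected in the analysis plan.

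**What to change.** In each Aim, state that:
- Time is categorical.
- The hypothesis test is the week-6 SR–HS difference in change from phase baseline. The sleep main effect across all visits is not used as a test.
- For two-visit outcomes, a woman-within-phase random effect is added to the woman effect or, to the same end, the within-woman difference in change is analysed.
- For weekly outcomes, a within-phase residual covariance is used (unstructured, or serial correlation plus woman-within-phase), or the within-woman week-6 change contrast is tested directly.
- The paired t and Wilcoxon tests use within-phase changes.
- Ambulatory blood pressure is compared between phases at endpoint only.

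No new data are needed. The cost is wording and some covariance parameters: one for the two-visit outcomes, and up to 7 × 8/2 = 28 for an unstructured seven-visit matrix, which may fail to converge with about 50 completers. Name the within-woman change contrast in advance as the fallback.
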